### **6.4 Reaction Management**

(1) Service providers/bank and credit union staff: Focus group participants might also experience distress when talking about their training experiences. The focus group facilitators are experienced and trained to address such situations. In our past experience with focus groups, there has never been an unmanageable situation of distress experienced by a focus group participant.

(2) Individuals with incarceration histories and mental health challenges: Potential risks to study participants may include distress by participating in an interview about their lives or discussing their financial health with financial coaches and Peer Wellness coaches. This sharing may evoke an array of responses, including emotional, psychological, cultural, or racial distress for some participants by recalling difficult experiences in their own life. The Financial and Peer Wellness coaches are trained and can assist the individuals in processing these emotions. The Research Assistant staff who will conduct interviews are also trained to address these situations. In our past experience, such events are very unlikely. If it is the case that a participant would like to talk further about their difficult

experience and need further support, they will be offered resources such as local hotlines, community based acute mental health service affiliate organizations in New Haven, (e.g., the Yale Department of Psychiatry), in addition to [name] who is a licensed clinical psychologist on our research team, and the research team's contact information. These resources will be made accessible with each of the Financial and Wellness coaches, and members of our research team.

## **6.5 Withdrawal Procedures**

Participants who wish to withdraw from the research study may do so by informing the PI or research staff. This may be done verbally or in writing.

## **6.6 Locations/Facilities**

- City of New Haven
- Connecticut Mental Health Center
- Yale University Program for Recovery and Community Health

# **7 Statistical Design**

## **7.1 Sample Size Considerations**

The primary outcome of interest is financial well-being. The primary hypothesis is that participants randomized to receive financial coaching plus peer support will have better financial well-being at 6-months compared to those who do not receive peer support. Based on prior research with low-income populations using financial well-being measures, we expect to observe a standardized effect size of 0.5. With 90% power and a two-sided type I error rate of 0.05, using a two-sample t-test (conservative), we will need 86 participants per arm (172 total) to detect the 0.5 standardized effect size. To account for a 15% missing data rate at the 6-month time point, we plan to randomize 204 participants (102 per group). For secondary outcomes at 6- and 12-months (e.g., employment, sense of belonging, social support, housing), we hypothesize that those receiving financial coaching plus peer support will perform better. Based on an effective sample size of 172 (at 6-months) and assuming an additional 10% missing data at 12-months (n=154), assuming a two-sided type I error rate of 0.01 (conservative to account for multiple testing), we will have 80% power to detect standardized effect sizes 0.53 and 0.56 for 6- and 12-months, respectively, for continuous outcomes, and absolute differences ranging from 23%-26% and 25%-27% for

6- and 12-months, respectively, for binary outcomes, for baseline rates in the treatment as usual group ranging from 20%-50%.

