Participants will be randomized to two arms: Arm #1 financial capability support = a) one-on-one financial coaching, which entails monthly or more frequent meetings with a financial coach; initial meetings are in person, and subsequent meetings can be via zoom, phone or in person, depending on the convenience for the client and b) access to safe and affordable financial services, which includes support with managing any existing bank accounts, or supporting a person to open a new overdraft-free account. Coaches can also help people to access other financial products such as free tax preparation (VITA), credit builder loans, online bank accounts, or other products recommended by our Justice Tech partner.

Arm #2 with peer support = in addition to financial capability support will also be offered one-on-one peer support from a trained Recovery Support Specialist...during the period they are receiving the intervention. Wellness coaches will provide weekly meetings (30 to 60 minutes duration).

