### 6.1.1 Data Collection

Data will be collected using the REDCap platform. Following informed consent, the participant will be asked to scroll to the next page to complete a demographic face sheet, then navigate through the online baseline measures by endorsing each item with their selected response (duration approximately 60 minutes). The measure packet will include a face sheet with demographic information, service utilization, SF-12V2, Quality of Life measure, ASI, ISEL-12, Adult State Hope Scale, Patient Activation Measure (PAM), Wellness in 8 Dimensions Inventory, Peer Support Service Satisfaction Survey, CMS\_AHC HRSN, Patient Health Questionnaire (PHQ9), SCL-90 Anxiety Subscale, Peer Support Provider Contact Log, Community Connections Index, Empowerment Scale, Financial Distress and Financial Wellbeing Scale, Financial Hardship Strain, Financial Skill Scale, The Financial Self-Efficacy Scale, Money Mismanagement Client Rated Assessment. The participant will be able to see their progress by viewing a completion bar located on the survey page. Upon completion of the baseline assessment, the participant will be asked to enter their email address for verification of e-gift card to receive their payment for participation in the online study. The participant may also choose to receive their payment in the form of a physical gift card or cash. Participants will have the option to have these interviews administered by the research staff or on their own.

These interviews will be administered at baseline, 6-months, and 12 months.

Participants (N=20) will also offered participate in qualitative interviews, a recorded informal conversation regarding their experiences. Questions will be developed with the help of the stakeholders CAB and submitted to IRB for approval prior to implementation. The qualitative interviews will be digitally audio/video recorded. These interviews will take place at the end of the 6-month and 12-month assessments.

In addition to the quantitative and qualitative interviews, the researchers will also be collecting notes from the CAB meetings, stakeholder meetings, focus groups, and peer workers notes and contacts.

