## 7.2 Planned Analyses

**Analysis:** All analyses will be performed according to intent-to-treat with an overall type I error rate of 5% (two- sided) using SAS (S, N) and (Project). All analyses will follow the design and account for stratification by gender. Parametric distributional assumptions (e.g., normality) will be checked and other distributions will be considered prior to transformations and non-parametric methods. Baseline descriptive statistics (e.g., means, standard deviations, frequencies, proportions) will be presented overall and by treatment group. No inferential statistics will be presented. Baseline variables that appear to be different between the two treatment groups will be adjusted for in sensitivity analyses. Linear mixed models utilizing all data (baseline, 6- and 12-month) adjusting for gender will be used to analyze the primary outcome. We will test the time by treatment group interaction term at the 10% level of significance. If this term is significant, we will utilize a contrast term at 6-months to test the primary hypothesis. If this term is not significant, we will use the time-averaged treatment difference to test the primary hypothesis. Generalized linear mixed models (e.g., log link for binary outcomes; identity link for continuous outcomes) adjusting gender will be used to analyze secondary outcomes. Like the primary outcome, we will test for treatment by time interactions at the 0.10 level. If significant we will use contrast at 6- and 12-months to assess for differences; if there is no interaction, then a time-averaged approach will be utilized, and we will have more power to detect the proposed effect sizes. To control for false discovery for secondary outcomes, we will use the Benjamini and Hochberg method. We will make attempts to limit the amount of missing data through stipend payments to participants, but we expect that we will encounter missing data. We will employ mixed models approaches, which utilize all available data and assume missing at random. We plan to assess the robustness of our results under a missing not at random assumption using pattern mixture models. We will also consider utilizing inverse probability weighting to account for missing data, if necessary. Exploratory analyses will focus on mediation analyses and explore tests of both the direct effect of treatment on the mediator and the indirect effect as well as the mediated effects of factors in between primary and secondary outcomes as predicted in the model (see Figure 2).

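### Sample size and primary model make no stated allowance for Arm 2 outcomes clustering by peer supporter, so the 90% power rests on an undisclosed assumption of zero clustering

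*Protocol*

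**What the plan says.** Participants are randomised individually, 1:1 (Protocol 6.2). Both arms receive financial coaching. Arm 2 "will also be offered one-on-one peer support from a trained Recovery Support Specialist" (section 4), with weekly meetings of 30 to 60 minutes. Section 4 does not say how many supporters there will be, how many participants each will carry, or how long peer support lasts; its Peer support paragraph uses both the singular and the plural.

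The primary hypothesis in 7.1 is that "participants randomized to receive financial coaching plus peer support will have better financial well-being at 6-months". The design inputs are: "we expect to observe a standardized effect size of 0.5"; "With 90% power and a two-sided type I error rate of 0.05"; and then "using a two-sample t-test (conservative), we will need 86 participants per arm (172 total". Finally, "To account for a 15% missing data rate at the 6-month time point, we plan to randomize 204 participants (102 per group". No ICC, caseload or design effect appears.

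For the analysis, 7.2 says: "Linear mixed models utilizing all data (baseline, 6- and 12-month) adjusting for gender will be used to analyze the primary outcome". Section 7.3 repeats the model with inmate status in place of gender. Neither version names a supporter effect. Section 6.1.1 lists a "Peer Support Provider Contact Log" among the data collected.

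**The concern.** This is a partially nested design. People are randomised one at a time, but in one arm they are then grouped under the person who delivers the intervention. Supporters may differ in skill or style, and if so the outcomes of people sharing a supporter are correlated, in Arm 2 only. Financial coaches serve both arms, so any clustering by coach should largely cancel in the comparison. Clustering by peer supporter does not.

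If that correlation is positive, the variance of the Arm 2 mean is larger than the independence formula gives. A standard error that ignores it is too small, the interval is too narrow, and a test with the right standard error has less power than 7.1 states. At stake is Objective 4, the value of adding peer support: an apparent benefit could partly reflect the particular supporters hired.

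**Working it through.** **Inputs from Protocol 7.1:** effect 0.5 SD; two-sided alpha 0.05; power 90%; 86 analysed per arm; 15% missing.

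**Inputs not in the documents (assumed):** number of supporters k from 2 to 10, equal caseloads; ICC from 0.01 to 0.05; total SD of 1 in both arms.

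**1. The plan's own figure.** The two-sample t-test needs 85.03 per arm, rounded up to 86, where power is 90.3%. Then 86/0.85 = 101.2, so 102 per arm and 204 in total. Both figures reproduce.

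**2. Allowing for clustering in Arm 2.**
- Design effect in Arm 2: DE = 1 + (86/k − 1) × ICC
- Standard error of the arm difference: SE = √((1 + DE)/86)
- Under independence: SE0 = √(2/86) = 0.1525
- Power of a test that uses the right SE: Φ(0.5/SE − 1.96)
- True type I error of a test that uses SE0: 2 × [1 − Φ(1.96 × SE0/SE)]

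Worked case, k = 4 and ICC = 0.05: DE = 1 + 20.5 × 0.05 = 2.025. SE = √(3.025/86) = 0.1876. Power = Φ(2.666 − 1.96) = 76%. Type I error = 2 × [1 − Φ(1.96 × 0.813)] = 11.1%.

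**3. The grid** (power of a valid test / true type I error of the test that ignores clustering):

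| Supporters | ICC 0.01 | ICC 0.02 | ICC 0.05 |
|---|---|---|---|
| 2 | 85% / 7.5% | 79% / 10.0% | 63% / 17.1% |
| 3 | 87% / 6.6% | 83% / 8.3% | 71% / 13.2% |
| 4 | 88% / 6.2% | 85% / 7.4% | 76% / 11.1% |
| 6 | 89% / 5.8% | 87% / 6.6% | 81% / 9.0% |
| 10 | 90% / 5.4% | 89% / 5.9% | 85% / 7.2% |

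At ICC 0 the same formulas return 5.0% and 90.6%, so nothing changes.

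**4. What the grid leaves out.** It uses a normal critical value. With few supporters the test has few degrees of freedom and power falls further: at k = 4 and ICC 0.05 the Satterthwaite degrees of freedom are about 6.6 and power is about 62% rather than 76%. In the other direction, the grid takes no credit for baseline or repeated measures.

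**5. Why the number of supporters matters.** With k fixed, the variance cannot fall below ICC/k however many participants are added. At k = 2 and ICC 0.05 that floor is 0.025, so SE is at least 0.158 and power at most Φ(0.5/0.158 − 1.96) = Φ(1.20), about 88%.

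**The case against.** Several points on the other side are sound.

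- **No arithmetic error.** A reader might infer that 86 or 204 is miscalculated. Both are right for the inputs given.
- **Few supporters is an inference.** The protocol gives no number. Its enrolment plan suggests a small team without establishing one: 118 people in year two means about 59 in Arm 2, or about 5 a month. If support lasted 6 months (an assumption), about 30 would be active at once, needing 15 to 30 contact hours a week. Turnover or part-time staff could raise the total number of supporters.
- **Power does not fall below 90% under every positive ICC.** With 2 supporters and ICC 0.001, DE = 1.042, SE = 0.1541 and power is 90.1%. With 10 supporters and ICC 0.01 the loss is about 1 point of power and under half a point of alpha.
- **The word *conservative* has a fair reading.** It plausibly means relative to the longitudinal model using all time points. That precision could recover power: if all variance shrank equally, the baseline correlation needed is √(1 − 2/(1 + DE)), which is 0.58 at k = 4 and ICC 0.05. This is generous, since supporter variation arises after baseline and need not shrink. It also does nothing for type I error.
- **An error rate above 5% is not automatic.** If peer support affects nobody, supporters create no variation and the simple test holds about 5%. The inflated figures need supporter effects that differ but average zero, and inference to supporters beyond those hired.
- **Peer support is only offered.** Under intent-to-treat, people who never engage dilute any clustering, which favours the lower ICCs.
- **The model may be completed in a statistical analysis plan.** Section 7.2 lists no random effects at all, so the absence of a supporter term is not a contradiction. A later document could supply it, but the power statement in 7.1 would still lack the allowance.

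**Conclusion.** The concern holds in a conditional form. Arm 2 alone is delivered by individual supporters, 7.1 assumes independence without saying so, and the primary model as written names no supporter effect. If the ICC is positive, power is overstated and the nominal 5% understates the true error rate, subject to the conditions above.

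For 2 to 10 supporters and ICC 0.01 to 0.05, power is about 90% down to 63%, and type I error about 5.4% to 17%. The lower end of the power range needs both very few supporters and an ICC of 0.05. The documents fix neither quantity, so they do not support a claim that the trial is underpowered or that its error rate is certain to exceed 5%. They do support asking for the assumption to be stated and tested.

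**What to change.** 1. In 7.1, state the expected number of supporters and the caseload, and report power over a range of ICCs beside the 90% figure.
2. Keep *conservative* only as a comparison with the longitudinal model, and say that it takes no account of clustering.
3. Record the supporter of every Arm 2 participant, using the existing contact log. Also record the supporter assigned to people who never attend, since they may have no log entry.
4. Pre-specify a sensitivity analysis of the primary contrast: a partially nested mixed model with a supporter random effect in Arm 2 only and small-sample degrees of freedom.

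**Cost:** no extra participants, a little analysis work, and a less favourable stated power. The sensitivity interval will be wider, and with few supporters the variance component will be imprecise. Small-sample degrees of freedom cost power even without clustering: with 4 supporters and ICC 0, power is about 85%. That is a reason to make it a sensitivity analysis rather than to replace the primary model.

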## 7.2 Planned Analyses

**Analysis:** All analyses will be performed according to intent-to-treat with an overall type I error rate of 5% (two- sided) using SAS (S, N) and (Project). All analyses will follow the design and account for stratification by gender. Parametric distributional assumptions (e.g., normality) will be checked and other distributions will be considered prior to transformations and non-parametric methods. Baseline descriptive statistics (e.g., means, standard deviations, frequencies, proportions) will be presented overall and by treatment group. No inferential statistics will be presented. Baseline variables that appear to be different between the two treatment groups will be adjusted for in sensitivity analyses. Linear mixed models utilizing all data (baseline, 6- and 12-month) adjusting for gender will be used to analyze the primary outcome. We will test the time by treatment group interaction term at the 10% level of significance. If this term is significant, we will utilize a contrast term at 6-months to test the primary hypothesis. If this term is not significant, we will use the time-averaged treatment difference to test the primary hypothesis. Generalized linear mixed models (e.g., log link for binary outcomes; identity link for continuous outcomes) adjusting gender will be used to analyze secondary outcomes. Like the primary outcome, we will test for treatment by time interactions at the 0.10 level. If significant we will use contrast at 6- and 12-months to assess for differences; if there is no interaction, then a time-averaged approach will be utilized, and we will have more power to detect the proposed effect sizes. To control for false discovery for secondary outcomes, we will use the Benjamini and Hochberg method. We will make attempts to limit the amount of missing data through stipend payments to participants, but we expect that we will encounter missing data. We will employ mixed models approaches, which utilize all available data and assume missing at random. We plan to assess the robustness of our results under a missing not at random assumption using pattern mixture models. We will also consider utilizing inverse probability weighting to account for missing data, if necessary. Exploratory analyses will focus on mediation analyses and explore tests of both the direct effect of treatment on the mediator and the indirect effect as well as the mediated effects of factors in between primary and secondary outcomes as predicted in the model (see Figure 2).

**Qualitative data analysis:** Transcriptions and field-notes will be analyzed and interpreted using qualitative thematic analysis procedures in which coding and sub-coding categories are derived iteratively from transcribed data, integrating inductive and deductive approaches. We will then integrate qualitative and quantitative findings to help us best understand the lived experience of financial difficulties related to incarceration for the target group, and the impact of the intervention on those difficulties. One way we will do this is by synthesizing the data to build participant profiles that identify constellations of demographic characteristics, incarceration histories and financial difficulties most associated with both improved financial well-being, and with lack of such improvement. We will do this by identifying the above associations using the quantitative analyses and using the qualitative data to probe more deeply into how those associations are experienced in people's lives.

**7.3** All analyses will be performed according to intent-to-treat with an overall type I error rate of 5% (two- sided) using SAS (Cary, NC) and R (R Project). All analyses will follow the design and account for stratification by inmate status. Parametric distributional assumptions (e.g., normality) will be checked and other distributions will be considered prior to transformations and non-parametric methods. Baseline descriptive statistics (e.g., means, standard deviations, frequencies, proportions) will be presented overall and by treatment group. No inferential statistics will be presented. Baseline variables that appear to be different between the two treatment groups will be adjusted for in sensitivity analyses. Linear mixed models utilizing all data (baseline, 6- and 12- month) adjusting for inmate status will be used to analyze the primary outcome. We will test the time by treatment group interaction term at the 10% level of significance. If this term is significant, we will utilize a contrast term at 6-months to test the primary hypothesis. If this term is not significant, we will use the time-averaged treatment difference to test the primary hypothesis. Generalized linear mixed models (e.g., log link for binary outcomes; identity link for continuous outcomes) adjusting for inmate status will be used to analyze secondary outcomes. Like the primary outcome, we will test for treatment by time interactions at the 0.10 level. If significant we will use contrast at 6- and 12- months to assess for differences; if there is no interaction, then a time-averaged approach will be utilized, and we will have more power to detect the proposed effect sizes. To control for false discovery for secondary outcomes, we will use the Benjamini and Hochberg method. We will make attempts to limit the amount of missing data through stipend payments to participants, but we expect that we will encounter missing data. We will employ mixed models approaches, which utilize all available data and assume missing at random. We plan to assess the robustness of our results under a missing not a random assumption using pattern mixture models. We will also consider utilizing inverse probability weighting to account for missing data, if necessary. Exploratory analyses will focus on mediation analyses and explore tests of both the direct effect of treatment on the mediator and the indirect effect as well as the mediated effects of factors in between primary and secondary outcomes as predicted in the model.

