### 6.2 Method of Assignment/Randomization (if applicable)

Randomization will take place at the individual level. Participants will be randomized to treatment as usual (regular FCS) or treatment as usual with peer support using a 1:1 allocation ratio. The randomization scheme will be generated by the study statistician and given to the data manager for implementation using the Research Electronic Data Captures (REDCap's) randomization module to maintain allocation concealment. The randomization will be stratified by gender and carried out using random permuted block sizes of 2,4, and 6. Participants will be randomly allocated after completion of the baseline assessment.

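### The pre-randomisation baseline score enters the primary model as an outcome wave, so the 6-month test gains little from it and the time-averaged fallback, read plainly, is diluted by a third or more

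*Protocol*

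**What the plan says.** Protocol section 7.1 sets the primary hypothesis at one time point: "participants randomized to receive financial coaching plus peer support will have better financial well-being at 6-months compared to those who do not receive peer support". For its size, "we expect to observe a standardized effect size of 0.5", and from that "we will need 86 participants per arm (172 total) to detect the 0.5 standardized effect size".

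Section 7.2 gives the model: "Linear mixed models utilizing all data (baseline, 6- and 12-month) adjusting for gender will be used to analyze the primary outcome". The time-by-treatment interaction is tested at the 10% level. If it is significant, a 6-month contrast tests the primary hypothesis. Otherwise: "If this term is not significant, we will use the time-averaged treatment difference to test the primary hypothesis". Secondary outcomes follow a similar rule; if there is no interaction, "then a time-averaged approach will be utilized, and we will have more power to detect the proposed effect sizes". The text numbered 7.3 repeats all this with inmate status in place of gender.

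On timing, section 6.2 says: "Participants will be randomly allocated after completion of the baseline assessment".

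Nowhere does the protocol make the baseline score a covariate, set the two arms to a common baseline mean, or say which visits the time average covers. Baseline variables that look different between arms are adjusted for only in sensitivity analyses.

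**The concern.** A score taken before allocation cannot be affected by treatment. Making it one of three levels of the time factor, with no constraint, has three consequences.

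- **The baseline score adds little precision.** In an unconstrained model with complete data, the 6-month contrast is simply the raw difference between arms at 6 months.
- **The interaction test changes meaning.** The true baseline difference is zero, so any treatment effect at follow-up is itself a time-by-treatment interaction. The absence of an interaction can be true only if there is no effect at all. The averaged route is therefore coherent only under the null, yet it is used to test the primary hypothesis.
- **The average is diluted.** Taken over the named waves, it mixes a known zero, plus any chance baseline imbalance, into the treatment effect.

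At stake are the precision of the primary comparison and, when the interaction is not significant, whether the reported number is the 6-month effect that section 7.1 describes.

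**Working it through.** **Inputs from the protocol.** Effect 0.5 SD, two-sided alpha 0.05, 90% power, 86 evaluable per arm; 15% missing at 6 months, hence 102 randomised per arm; a further 10% missing at 12 months, n = 154, or 77 per arm (section 7.1). Interaction test at 0.10 (section 7.2).

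**Assumptions.** The protocol gives no within-person correlation ρ. I take 0.3, 0.5 and 0.7, equal variances at all waves and the same correlation between any two waves.

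**Step 1, the plan's own figure.** The exact two-sample t-test has power 0.8999 at 85 per arm and 0.9032 at 86, so 86 is right. 86/0.85 = 101.2, rounded up to 102 per arm, 204 in all. The sample size reproduces.

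**Step 2, three-wave average, complete data.** Expected value (0 + 0.5 + 0.5)/3 = 0.333. The SD of a person's three-wave mean is √((1+2ρ)/3). Power is Φ(effect/(SD × √(2/86)) − 1.96), with √(2/86) = 0.1525. At ρ = 0.5: 0.333/(0.816 × 0.1525) = 2.68, and Φ(0.72) = 76%.

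| Quantity | ρ = 0.3 | ρ = 0.5 | ρ = 0.7 |
|---|---|---|---|
| Three-wave average, power | 85% | 76% | 69% |
| Raw 6-month difference, power | 91% | 91% | 91% |
| 6- and 12-month average, no baseline covariate, power | 98% | 97% | 95% |

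The raw 6-month difference has SD 1. The 6- and 12-month average has SD √((1+ρ)/2) and expected value 0.5.

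**Step 3, planned missingness.** With 102, 86 and 77 per arm at the three waves and generalised least squares weights for a constant effect, baseline takes 41%, 42% and 43% of the weight. At ρ = 0.5 the weights are 0.422, 0.310 and 0.268, so the average is 0.5 × (0.310 + 0.268) = 0.289. Across the three correlations it is 0.296, 0.289 and 0.283, with power 79%, 69% and 60%.

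**Step 4, how often this route is taken.** For effects (0, d, d) the 2-df interaction test has noncentrality d² × (2/3) × 43/(1−ρ). For d = 0.5 that is 10.2, 14.3 and 23.9. Simulation of the whole two-stage rule (400,000 replicates, 86 per arm) gives:

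| True effect at 6 and 12 months | Quantity | ρ = 0.3 | ρ = 0.5 | ρ = 0.7 |
|---|---|---|---|---|
| 0.5 | averaged route taken | 10.6% | 3.4% | 0.2% |
| 0.5 | overall power | 91% | 91% | 91% |
| 0.3 | averaged route taken | 49% | 36% | 16% |
| 0.3 | mean estimate on that route | 0.20 | 0.20 | 0.20 |
| 0.3 | overall power | 52% | 49% | 49% |

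**Step 5, secondary rule.** At alpha 0.01, d = 0.53 and ρ = 0.5, the three-wave average has 0.353/0.1245 = 2.84, and Φ(2.84 − 2.576) = 60%. The 6-month contrast has 0.53/0.1525 = 3.48, and Φ(3.48 − 2.576) = 82%. The averaged route is taken in about 2% of trials, and overall power stays at about 82%.

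**Step 6, after the change.** With baseline as a covariate the 6-month SD becomes √(1−ρ²): 0.954, 0.866 and 0.714. Power at 6 months is 93%, 97% and 99.6%. With a common baseline mean and the planned missingness the figures are the same.

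**The case against.** The strongest reply is that the protocol leaves the point undefined rather than wrong. A mixed model using all three waves also describes a model with a common baseline mean, or one with a change-from-baseline contrast, and contrast coefficients may be left to a statistical analysis plan, which was not available here. The secondary contrasts are placed at 6 and 12 months, which suggests the authors think of effects after baseline. If the average covers only those visits, the sentence promising greater power is correct (95% to 98% against 91%).

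Much of this stands. The document fixes neither the form of the 6-month contrast nor the visits averaged, so the power sentence fails only if baseline is in the average. It is also too strong to say that the 6-month contrast ignores baseline. That is exact only for an unconstrained contrast with complete data. With the planned missingness baseline adds a little (91% to 93%), and a change-from-baseline contrast uses it fully, with power 79%, 91% and 99% at ρ = 0.3, 0.5 and 0.7. That spread is itself a reason to state the form.

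A reader might also take 69% to 85%, or 60% for secondary outcomes, as the power of the trial. They are not: they apply only on the averaged route, which is rarely taken at the design effect. The raw 6-month difference is unbiased and delivers the stated 90%. Chance baseline imbalance is minor too: its SD is √(2/102) = 0.14, and one third of that is about 0.05.

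The reply does not remove the point. Sections 7.2 and 7.3 themselves name the waves, the single adjustment and both routes, and nothing in them keeps the pre-randomisation wave out of the average.

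**Conclusion.** The point holds in a limited form. On the plain reading, the plan treats a pre-randomisation score as an outcome, gains little precision from it at 6 months, and falls back on an average that estimates about two thirds of an equal 6- and 12-month effect, or 57% to 59% of it with the planned dropout (0.283/0.5 to 0.296/0.5).

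At the design effect of 0.5 this costs almost no overall power. The dilution matters when the true effect is smaller: at 0.3 the averaged route is taken in 16% to 49% of trials and reports 0.20. Even there the main harm is to the estimate, since overall power (49% to 52%) is close to that of always using the 6-month contrast (about 50%). The documents do not support a claim that the trial is underpowered.

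The main loss is precision already paid for: about 91% power at 6 months where 93% to 99.6% is available. The sizes rest on the assumed correlation of 0.3 to 0.7, equal variances and, for the dilution, equal effects at 6 and 12 months. If the 12-month effect were 0.25 or 0, the equally weighted three-wave average would be 0.25 or 0.167.

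**What to change.** Make the same changes in section 7.2 and in the repeated text numbered 7.3:

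1. Either make 6 and 12 months the only responses, with the baseline score as a covariate, or keep all three waves and constrain the arms to a common baseline mean.
2. Limit the treatment-by-time terms, and any time average, to 6 and 12 months.
3. Define the 6-month contrast on that model as the test of the primary hypothesis in section 7.1.
4. Do the same for secondary outcomes measured at baseline.
5. Tie the sentence about greater power to the average of the 6- and 12-month differences.

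The cost is analysis wording only. No new data, visits or participants are needed. Because it defines the primary test, it should be settled before outcome data are analysed by arm.
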